5.2.1. Visit Windows

At each specified study visit, procedures will be performed according to the schedule of activities ([Appendix 5](#)).

A study visit may be scheduled on any day within a specified study week. For any given day within the study week, the visit window is ± 5 days (ie, 5 days before or after the given day) unless otherwise stated.

Study drug supplies must be taken into account when scheduling visits during windows. Procedures for a given visit may be split across the window to allow for drug resupply and completion of study procedures.

5.2.2. Week 1, Day 1

Study site personnel will access the IWRS to assign a randomization ID number to a study participant. This number will be used to identify the patient for the remainder of the study.

Day 1 procedures are listed in [Table 2](#). Study site personnel should ensure that an approved Randomization Authorization Form is in the patient’s file before proceeding with day 1 procedures.

The blood samples for central laboratory evaluations should be collected and the patient questionnaires should be completed before the first dose of study drug to establish baseline.

If study drug cannot be administered on the same day as randomization, the patient must come to the clinic within 3 business days after randomization for the required procedures and initiation of study treatment. Day 1 is the day of randomization regardless of the date of the first dose of study drug. Note that time of first dose will be recorded in the electronic data capture (EDC) system.

Table 2. Week 1, Day 1 Procedures

Activity/Assessment	Comment
Randomization	Access the IWRS to assign randomization ID number and study drug treatment. May occur up to 3 business days before the day of first dose.
General Activities	
Vital signs and brief physical examination	May skip these assessments if performed within prior 7 days. Measure blood pressure, heart rate, temperature, and weight. Perform symptom-directed examination and investigate any new abnormalities.
ECOG performance status	Refer to Table 13 .
BPI-SF, FACT-P, EQ-5D-5L, and QLQ-PR25 questionnaires	Complete BEFORE the first dose of study drug. Refer to Appendix 1 , Appendix 2 , Appendix 3 , and Appendix 4 .
Adverse events review	Record adverse events that occurred in enrolled patients in the patient’s source documents.
Concomitant medications review	Record any new medications or changes in ongoing medications.

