3.4. Baseline Variables

3.4.1. Study Drug, Study Treatment, and Baseline Definitions

The date of first dose (start date) of study treatment in the combination arms is the earliest date of non-zero dosing for each of the study drugs (enzalutamide/placebo or leuprolide).

The date of first dose (start date) of study treatment in the enzalutamide monotherapy arm is the earliest date of non-zero dosing of enzalutamide.

The date of last dose of study treatment in the combination arms is the latest date of non-zero dosing for each of the study drugs.

The date of last dose of study treatment in the enzalutamide monotherapy arm is the latest date of non-zero dosing of enzalutamide.

Definition of Baseline:

No windowing will be applied when defining baseline. For example, the protocol requires safety assessments to be performed within 28 days prior to randomization; however, values outside this window will not be excluded when determining baseline assessments. Any deviations from the protocol specified window will be documented as protocol deviations.

Definition of baseline for efficacy and baseline analyses

The last measurement prior to randomization will serve as the baseline measurement for efficacy and baseline analyses.

Definition of baseline for PRO

Per protocol, the first PRO assessment is planned to occur prior to dosing on Day 1; therefore, the last measurement on or prior to the day of first dose of study treatment (on or prior to randomization for patients randomized but not dosed) will be used as the baseline measurement.

Definition of baseline for safety analyses

The last available assessment on or prior to the date of first dose of study treatment (or prior to randomization for patients randomized but not dosed) is defined as the 'baseline' value or 'baseline' assessment for safety analyses. If an assessment is planned to be performed prior to the first dose of study treatment in the protocol and the assessment is performed on the same day as the first dose of study treatment, it will be assumed that it was performed prior to study treatment administration, if assessment time is not collected or is missing. If assessment times are collected, the observed time point will be used to determine pre-dose on study Day 1 for baseline calculation (this only applies for safety). Unscheduled assessments will be used in the determination of baseline.

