6.2.2. Time to PSA Progression

Only results from PSA samples taken before the initiation of any new prostate cancer therapy and after the start of study drug will be considered.

PSA progression is defined in Section 3.2.1 as the date that a \geq 25% increase and an absolute increase of \geq 2 µg/L (2 ng/mL) above the nadir (or baseline for patients with no PSA decline by week 25) that is confirmed by a second consecutive value at least 3 weeks later. The date of PSA progression is the first date the PSA progression is observed. For patients who have suspended treatment at week 37 and later reinitiated treatment, baseline will be defined as the last PSA assessment prior to or on the date of reinitiation. The date of PSA progression is the first date the PSA progression is observed.

PSA progression is only defined during active study treatment; therefore, patients meeting PSA progression during the suspension period will be censored unless the PSA progression criteria are subsequently met following treatment reinitiation. Time to PSA progression will be censored on the date of the last PSA sample taken. Patients with PSA progression after 2 or more consecutive missed PSA assessments (ie, time interval >6 months or 182 days between 2 consecutive PSA samples) will be censored on the date of last PSA assessment prior to the missed assessments. In patients with no baseline PSA and patients with no postbaseline PSA results, time to PSA progression will be censored on the date of randomization.

Time to PSA progression will be compared between treatment groups using a 2-sided stratified log-rank test.

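### Time to PSA progression: the SAP's baseline rule can pass over the Day 1 PSA, and its 182-day missed-sample rule misfires when only week 25 is missed

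*SAP*

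**What the plan says.** **Baseline.** SAP 3.4.1 states for efficacy: "The last measurement prior to randomization will serve as the baseline measurement for efficacy and baseline analyses". For patient-reported outcomes the same section uses "the last measurement on or prior to the day of first dose of study treatment". For safety it also works from the first dose, and it limits the use of recorded clock times on Day 1 to the safety baseline.

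Protocol 5.2.2 says that the central laboratory blood samples, which include PSA (Table 2), "should be collected and the patient questionnaires should be completed before the first dose of study drug to establish baseline". It adds: "Day 1 is the day of randomization regardless of the date of the first dose of study drug". If drug cannot be given that day, "the patient must come to the clinic within 3 business days after randomization for the required procedures and initiation of study treatment".

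**Samples that count.** SAP 6.2.2: "Only results from PSA samples taken before the initiation of any new prostate cancer therapy and after the start of study drug will be considered".

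**Missed samples.** SAP 6.2.2 censors a PSA progression that follows two or more consecutive missed PSA assessments at the last PSA before the gap. It explains the condition as "ie, time interval >6 months or 182 days between 2 consecutive PSA samples".

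**Schedule.** Protocol Appendix 5 places PSA at screening, Day 1, week 25, week 36, week 37, week 49 and every 12 weeks after that. There is none at week 13.

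**The concern.** The protocol takes a Day 1 PSA for the stated purpose of fixing baseline, but the SAP's efficacy rule looks to a time before randomization. A Day 1 sample drawn after randomization and before dosing is too late to be baseline under 3.4.1 and too early to be follow-up under 6.2.2. Baseline is then the screening value. Men enter this trial with rising PSA, so an older value tends to be lower. In a man without a decline by week 25, part of the rise needed for progression would then have occurred before treatment began.

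The missed-sample rule is stated in words and in days, and the two disagree in the first interval. A programmer who follows the days censors a man who missed one sample; one who follows the words does not.

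Time to PSA progression is an alpha-controlled key secondary endpoint in both comparisons. It is also a component of time to castration resistance (SAP 6.3.6).

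**Working it through.** **Inputs.** Study days from Appendix 5: Day 1, week 25 = 169, week 36 = 246, week 37 = 253, week 49 = 337, then every 84 days. Visit window ±5 days. Screening day -28 to day -1, with no day 0 (Protocol 5.1). One month = 30.4375 days (SAP 5.2.6). Doubling time at entry at most 9 months (Protocol 4.1). Progression needs a rise of at least 25% and at least 2 ng/mL (SAP 3.2.1.2).

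**1. The SAP's figure.** 6 × 30.4375 = 182.6 days, and 2 × 84 + 14 = 182 days. So 182 days is two 12-week intervals plus two weeks, a sensible upper limit for one missed visit on a 12-week schedule.

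**2. The rule against the schedule.**

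| Missed | Gap between samples | Days (range with windows) | Over 182? |
|---|---|---|---|
| One visit, last sample at week 37 or later | 2 × 84 | 168 (158–178) | No |
| Two visits, last sample at week 37 or later | 3 × 84 | 252 (242–262) | Yes |
| Week 25 only | 246 − 1 | 245 (240–250) | Yes |
| Weeks 25 and 36 | 253 − 1 | 252 (247–257) | Yes |
| Weeks 36 and 37 | 337 − 169 | 168 (158–178) | No |

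The first two rows show the rule working. The third shows it triggering after one missed sample. Because weeks 36 and 37 are 7 days apart and are best counted as one assessment, the fourth row is also a single miss, and the fifth is a single miss correctly left alone.

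The 245 days assume that the Day 1 sample opens the first gap. If the screening sample does, the gap is longer, up to 246 + 28 − 1 = 273 days. If no pre-dose sample counts, the first gap has no starting point. The SAP does not say which applies.

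**3. Growth between screening and Day 1.** From day -28 to Day 1 is 28 days. Under exponential growth the ratio of Day 1 to screening PSA is 2^(28 / (30.4375 × doubling time in months)):

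- 9 months: 1.073 (+7.3%)
- 6 months: 1.112 (+11.2%)
- 3 months: 1.237 (+23.7%)

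Seen from Day 1, the screening value is lower by 1 − 1/1.073 = 6.8% to 1 − 1/1.237 = 19.1%. A draw on day -14 gives +3.6% at 9 months and +11.2% at 3 months. Eligibility sets no lower limit on doubling time; at 2 months the 28-day growth is 37.6%.

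**4. Effect on the progression threshold.** The 2 ng/mL condition binds below a baseline of 2 / 0.25 = 8 ng/mL. Two illustrative screening values, with a day -28 draw and a 3-month doubling time:

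- Screening 1 ng/mL, Day 1 1.24. Threshold 1 + 2 = 3.00 from screening, 1.24 + 2 = 3.24 from Day 1.
- Screening 10 ng/mL, Day 1 12.37. Threshold 1.25 × 10 = 12.50 from screening, 1.25 × 12.37 = 15.46 from Day 1.

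At 10 ng/mL and a 9-month doubling time the thresholds are 12.50 and 1.25 × 10.73 = 13.42. The shift is material only at higher PSA with fast doubling and an early screening draw.

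**The case against.** **The test has been run.** SAP 5.1.2 sets the OS alpha at 0.05 from the actual results. Under step 5 of SAP 5.1.3 that requires all the earlier key secondary tests to have succeeded in both comparisons. Only OS remains for formal testing, and the study is unblinded. This stands. A reader might infer that the flaw still threatens the testing hierarchy; the documents do not support that. It also rules out replacing the tested result.

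**The Day 1 value is not lost in every man.** Table 2 does not fix the order of the blood draw and the IWRS call, so a sample drawn first could count as before randomization. This stands. The exclusion is certain only when the draw follows randomization, as at a dosing visit on a later day.

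**The 182-day limit is not wrong in general.** This stands from week 37 on. The week 36 and 37 example is no failure once those visits count as one.

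**A gap of up to 196 days from screening to week 25 with no missed visit (169 + 28 − 1) cannot be claimed.** It is tempting, but it needs the screening sample to open the gap. SAP 6.2.2 restricts attention to samples after the start of drug, and its wording concerns missed assessments. It shows only that the starting sample should be named.

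**Few men are exposed.** Baseline is the reference only in non-suspended men with no decline by week 25; reinitiated men are re-baselined (SAP 3.2.1.2). In the single-arm monotherapy study in Protocol 1.2, 93% had a PSA fall of at least 80% at week 25. This stands, though that study says nothing about leuprolide alone.

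**Censoring after 245 unobserved days is defensible.** It may be, but it is not the two-miss rule that the SAP states in words.

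**Conclusion.** Both points hold in limited form.

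- **Baseline.** On a date-based reading, and certainly when the draw follows randomization, the efficacy baseline is the screening PSA. The Day 1 value would be about 7% to 24% higher for a day -28 draw at doubling times of 9 to 3 months, assuming exponential growth, and less for later draws. Comparing 24% with the 25% threshold alone would overstate this, because the 2 ng/mL condition governs below 8 ng/mL. Besides the men without a decline, it touches the baseline PSA summary (SAP 6.7.1) and the PSA subgroup (SAP 6.6), which SAP 6.2.4 reuses at the final OS analysis.
- **Missed samples.** The conflict is confined to the first interval: 245 days after one missed sample, given that Day 1 opens the gap. A week-36 progression would then be censored at Day 1, leaving that man almost no follow-up in the analysis.

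The documents give no count of affected men; it is probably small. Nothing in them shows a difference between arms, and a bias in the reported comparison should not be inferred.

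**What to change.** 1. In SAP 3.4.1, define baseline PSA as the last central value on or before the first dose, or on or before randomization for men never dosed. State that this sample opens the first gap in SAP 6.2.2.
2. In SAP 6.2.2, count missed scheduled PSA assessments from Appendix 5, with weeks 36 and 37 as one, and censor only after two or more consecutive misses. Alternatively, keep 182 days and set a separate day limit for the interval before week 36.
3. Leave the formally tested result in place. Record the change as a clarification, re-run time to PSA progression as a sensitivity analysis, and state in the CSR which baseline and gap rules were used and how many men change status in each arm.

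The Day 1 PSA is already collected, so the cost is a paragraph of SAP text and one re-run derivation. The re-run is post hoc and should be labelled so.

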3.4.2. Stratification

Randomization is stratified by the following, as recorded in the Interactive Response Technology (IRT):

- Screening PSA ≤ 10 ng/mL versus > 10 ng/mL,
- PSA doubling time ≤ 3 months versus >3 to ≤ 9 months,
- Prior hormonal therapy versus no prior hormonal therapy

Unless otherwise specified, stratified analyses will utilize strata as defined in the randomization system.

3.5. Safety Endpoints

Safety will be assessed through adverse event (AE) reporting, laboratory and vital sign assessments. AEs will be graded by the investigator according to the Common Terminology Criteria for Adverse Events (CTCAE) version 4.03 and coded using the Medical Dictionary for Regulatory Activities (MedDRA) version in use at the time of database release.

Safety endpoints will be summarized based on the on-treatment period, modified treatment period, or re-initiation treatment period as specified.

On-Treatment Period

The on-treatment period is defined as the time from the date of first dose of study treatment through a minimum of 30 days after last dose of study treatment, or the start day of new antineoplastic drug therapy -1 day, where the last dose of study treatment is the final dose after any suspension period due to undetectable PSA. Adverse events occurring on the same day as the first dose of study treatment will be considered to have occurred during the on-treatment period. All other assessments which occur on the same day as the first dose of study treatment will be considered baseline assessments (see Section 3.5).

Safety data collected outside the on-treatment period as described above will be listed but not summarized.

Modified Treatment Period

For patients whose treatment is suspended due to undetectable PSA at week 36 the modified period is defined as the period of time of study drug exposure starting from the date of the first dose of study drug through 30 days after last dose prior to the treatment suspension PLUS the time period starting from date of first dose at study drug reinitiation through a minimum of 30 days after last dose of study treatment, or the start day of new antineoplastic drug therapy -1 day. If date of first dose at study drug reinitiation is earlier than 30 days after last dose prior to the treatment suspension, then the modified treatment period is the same as that on-treatment period.

For all other patients the modified treatment period is the same as the on-treatment period.

Reinitiation Treatment Period

The reinitiation treatment period is defined only for patients who suspend treatment due to undetectable PSA at week 36 and subsequently reinitiate treatment and is defined as the time

period starting from date of first dose at study drug reinitiation through minimum 30 days after last dose of study treatment, or start day of new antineoplastic drug therapy -1 day.

Treatment-Emergent Adverse Events

Treatment-emergent adverse events (TEAEs) are those events with onset dates occurring during the on-treatment period for the first time

Modified Treatment-Emergent Adverse Events

Modified treatment-emergent adverse events (mTEAEs) are adverse events occurred during the modified treatment period (ie, events occurring or worsening during the treatment suspension period after 30 days of last dose prior to treatment suspension (and prior to treatment suspension if applicable) are excluded).

Reinitiation Treatment-Emergent Adverse Events

Reinitiation treatment-emergent adverse events (rTEAEs) are adverse events occurred for the first time during the dosing period after suspension and reinitiation of study treatment as defined by the reinitiation treatment period.

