7.2. Concomitant Therapy

Concomitant medications will be assessed at all clinic visits. All concomitant medications, including analgesic medications and opiates (including opioid-containing medications), must be recorded on the appropriate case report form. If the use of any medication during the study is due to an adverse event, the adverse event must be recorded on the adverse event case report form and in the patient's source documents.

Initiation of bisphosphonates or denosumab for the prevention of bone metastases is prohibited following randomization; however, treatment with these agents should continue at a stable dose if initiated at least 4 weeks before randomization. Initiation of bisphosphonates or denosumab at doses to treat osteoporosis is allowed if a diagnosis of osteoporosis is made during the study.

Patients are strongly encouraged to obtain an adequate intake of dietary calcium (at least 1000 mg per day, including supplements if necessary) and vitamin D (at least 800-1000 international units per day for adults 50 years of age and older) and to engage in regular exercise to maintain muscle strength and bone density.

Initiation of abiraterone or antiandrogen therapy is prohibited before radiographic disease progression.

Randomized study drug treatment must be permanently discontinued upon initiation of anti-cancer chemotherapy or antiandrogen therapy (eg, bicalutamide, nilutamide, or

flutamide). Note: Localized anticancer therapy (eg, topical treatment of non-melanoma skin malignancy, intravesical Bacillus Calmette-Guerin [BCG] treatment) may be acceptable upon prior Sponsor and Investigator agreement and written Sponsor approval.

Patients who discontinue study drug treatment due to initiation of any such therapy will remain in the study, complete safety follow-up per [Section 5.4](#), and then begin long-term follow-up assessments every 12 weeks thereafter based on the 12-week visit schedule determined at randomization per [Section 5.5](#).

The following treatments are allowed:

- Blood transfusions and growth factor support per standard of care and institutional guidelines;
- Corticosteroids for nonprostate cancer indication;
- Pain therapy per standard of care and institutional guidelines;
- Palliative procedures to treat skeletal-related events.

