8.1.5. Reporting SAEs to Pfizer Safety

All SAEs occurring in a subject during the active collection period are reported to Pfizer Safety on the CT SAE Report Form.

SAEs occurring in a subject after the active collection period has ended are reported to Pfizer Safety if the investigator becomes aware of them; at a minimum, all SAEs that the investigator believes have at least a reasonable possibility of being related to investigational product must be reported to Pfizer Safety.

Follow up by the investigator continues throughout and after the active collection period and until the event or its sequelae resolve or stabilize at a level acceptable to the investigator, and Pfizer concurs with that assessment.

If a patient begins a new anticancer therapy, SAEs occurring during the above-indicated active collection period must still be reported to Pfizer Safety irrespective of any intervening treatment.

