8.1.6. Recording Non-serious AEs and SAEs on the Case Report Form

During the active collection period, both non-serious AEs and SAEs are recorded on the case report form.

Follow-up by the investigator may be required until the event or its sequelae resolve or stabilize at a level acceptable to the investigator, and Pfizer concurs with that assessment.

If a patient begins a new anticancer therapy, the recording period for non-serious AEs ends at the time the new treatment is started; however, SAEs must continue to be recorded on the case report form during the above-indicated active collection period.

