10.5. Safety Analyses

All safety analyses will be performed using the safety population.

Safety analyses will be summarized by treatment. Safety will be evaluated by the incidence of serious adverse events, incidence and severity of adverse events, incidence of permanent treatment discontinuation due to adverse events, and incidence of new clinically significant changes in clinical laboratory values and vital signs.

The treatment-emergent period is defined as the duration of time from the date and time of the first dose of any randomized study drug treatment (enzalutamide plus leuprolide, enzalutamide monotherapy, or placebo plus leuprolide) through 30 days after the last dose of randomized study drug treatment (permanent treatment discontinuation). The treatment-emergent period will include the period from first dose through potential protocol-specified suspension and potential resumption of study drug treatment before permanent treatment discontinuation. Safety data collected following 30 days after study drug suspension and during the time off study drug treatment will be analyzed and described.

Adverse events will be coded according to the Medical Dictionary for Regulatory Activities (MedDRA) and tabulated by system organ class and by preferred term within each system organ class. Tabular summaries will include the incidence overall (number and percentage of patients with treatment-emergent adverse events classified by system organ class and preferred term); incidence by intensity (severity graded according to the CTCAE, version 4), causality, seriousness, and outcome (eg, leading to discontinuation of study drug); and other presentations as appropriate.

Serious adverse events occurring before study treatment will be tabulated separately if considered related to study procedure.

Patients with the same adverse event reported more than once will be counted once at the maximum severity or strongest relationship to study drug.

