6.8.1. Adverse Events

The severity of all adverse events is to be evaluated by the investigator based on the NCI CTCAE version 4.03. All adverse events will be coded to preferred term (PT) and system organ class (SOC) using MedDRA version in use at the time of database release.

TEAEs will be summarized by PT and/or SOC, toxicity grade, and relationship to study treatment. An event will be considered treatment related if the investigator considered the event related to one or both of study drugs given in combination. The treatment related summaries will be separated for one or both study drugs when given in combination.

Separate summaries will be provided for serious TEAEs regardless of causality and serious TEAE related to study treatment.

Separate summaries will be provided for TEAEs (regardless of relationship to study treatment):

- Leading to permanent discontinuation from enzalutamide,
- Leading to permanent discontinuation form leuprolide,
- Leading to enzalutamide dose interruptions,
- Leading to leuprolide dose interruptions,
- Leading to enzalutamide dose reductions, and
- Leading to leuprolide dose reductions.

mTEAEs and rTEAEs defined as in Section 3.5 will be summarized by toxicity grade and relationship to study treatment. Separate summaries will also be provided for:

- Serious mTEAE regardless of causality,
- Serious mTEAE related to study treatment,
- Serious rTEAE regardless of causality, and
- Serious rTEAE related to study treatment.

Patients with multiple occurrences of events for a given PT, SOC will only be counted once.

Adverse event time-adjusted rates will be calculated as the number of occurrences of event divided by the number of patient-years of treatment-emergent (for the corresponding treatment emergent period)surveillance for each treatment group. Patients can have more than 1 occurrence of each event.

Additionally, Kaplan-Meier methods will be used to display the time to the first Grade 3 or higher TEAE by treatment group. Patients who are not known to have had Grade 3 or higher TEAE by the analysis cutoff date are censored at the date last known to be Grade 3 or higher TEAE-free. Kaplan-Meier methods will also be used to display the time to the first SAE by treatment group. Patients who are not known to have had SAE by the analysis cutoff date are censored at the date last known to be SAE-free.

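### SAP 3.5 can close the on-treatment period at the start of new antineoplastic therapy, so SAEs that the protocol counts as treatment-emergent and requires sites to collect are left out of the serious-TEAE tables

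*SAP*

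**What the plan says.** **SAP.** Section 3.5 starts the on-treatment period at first dose and runs it "through a minimum of 30 days after last dose of study treatment, or the start day of new antineoplastic drug therapy -1 day". The modified and reinitiation treatment periods end in the same way. Section 3.5 adds: "Safety data collected outside the on-treatment period as described above will be listed but not summarized". TEAEs are "those events with onset dates occurring during the on-treatment period for the first time". The serious-event tables in SAP 6.8.1 are built on that flag: "Separate summaries will be provided for serious TEAEs regardless of causality and serious TEAE related to study treatment".

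**Protocol.** Section 10.5 ends the treatment-emergent period "through 30 days after the last dose of randomized study drug treatment (permanent treatment discontinuation". It names no earlier end at new therapy. Section 8.1.6 stops recording of non-serious AEs when a new anticancer therapy starts, but "SAEs must continue to be recorded on the case report form during the above-indicated active collection period". Section 8.1.5 says the same of expedited reporting: "SAEs occurring during the above-indicated active collection period must still be reported to Pfizer Safety irrespective of any intervening treatment". Under section 8.1.4 the active collection period lasts at least 30 days after the last administration. Section 8.5.5.2 has fatal events reported as SAEs through 30 days after permanent discontinuation.

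**The concern.** The protocol separates two kinds of event. Once a new anticancer therapy begins, non-serious events are no longer recorded, while serious events are recorded to the end of the 30-day window. The SAP applies one cut to both. For non-serious events this matches collection. For serious events it discards data that sites were required to provide and that Protocol 10.5 classes as treatment-emergent.

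At stake is whether the main serious-event tables show what the protocol says they will show. Protocol 5.4 foresees antineoplastic treatment starting before the safety follow-up visit, so the overlap is not hypothetical. Safety analyses after protocol amendment 5 are still planned (SAP 6.8), so the definition still matters.

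**Working it through.** The plan gives no figure to reproduce, so the check sets the definitions side by side and then counts days.

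**Step 1: the two windows after last dose.**

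| | End of window | Cut at new therapy? |
|---|---|---|
| Protocol 10.5, treatment-emergent period | last dose + 30 days | no |
| Protocol 8.1.4–8.1.6, SAE collection | at least last dose + 30 days | no |
| Protocol 8.1.6, non-serious AE recording | as above, or start of new therapy | yes |
| SAP 3.5, all three treatment periods | last dose + 30 days, or day before new therapy | yes |
| SAP 6.8.2, deaths soon after treatment | last dose + 30 days | no |

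**Step 2: trace one event.** Take an SAE that starts on or after the first day of new therapy and within 30 days of last dose.
- Protocol 8.1.5 and 8.1.6: it must be reported and recorded.
- Protocol 10.5: it is treatment-emergent.
- SAP 3.5, with the earlier date governing: its onset is outside the on-treatment period, so it is not a TEAE.
- SAP 6.8.1: it is not in the serious-TEAE tables. Under SAP 3.5 it appears only in a listing.

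**Step 3: days lost.** Let new therapy start d days after last dose, with d from 1 to 30. The protocol window holds 30 post-dose days. The SAP window keeps days 1 to d − 1. Days lost = 30 − (d − 1) = 31 − d.

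| d | Days kept (d − 1) | Days lost (31 − d) | Share of 30 days |
|---|---|---|---|
| 1 | 0 | 30 | 100% |
| 8 | 7 | 23 | 77% |
| 15 | 14 | 16 | 53% |
| 30 | 29 | 1 | 3% |
| 31 or later | 30 | 0 | 0% |

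**Step 4: which end point governs.** SAP 3.5 joins the two with *or* and does not add *whichever occurs first*. The earlier-of reading is the natural one, but the reference to a minimum of 30 days fits it poorly. Two programmers could derive different flags.

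**Step 5: related wording.** SAP 6.8 sends the reader to section 5.2.5 for the on-treatment period. That section gives treatment durations but does not define the period; section 3.5 does. SAP 6.8.3 and 6.8.5 summarize laboratory and vital-sign data over a treatment-emergent period, a term that SAP 3.5 does not define and Protocol 10.5 does. Two windows could therefore operate in one report.

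**The case against.** **The SAP may depart from the protocol, and the cut has a purpose.** SAP section 2 allows changes to protocol plans, and stopping at a new cancer drug avoids charging that drug's toxicity to study drug. Protocol 8.1.5 and 8.1.6 govern collection, not tabulation. All of this is fair. But Protocol 10.5 does govern analysis, and the SAP's change table records only clarifications of the modified treatment period and duration, not this departure. Attribution can be handled by a footnote or by keeping the truncated table as well.

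**Fatal events are covered elsewhere.** This largely stands. SAP 6.8.2 tabulates all deaths, and deaths within 30 days of last dose, with no cut at new therapy. The Kaplan-Meier display of time to first SAE in SAP 6.8.1 is not worded as treatment-emergent. The loss is from the TEAE and serious-TEAE tables, not from every output, and deaths need no new window.

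**The effect may be small.** This cannot be excluded. Nothing is lost if new therapy starts 31 or more days after last dose. In the open-label period, safety follow-up moves to just before the new therapy and AE collection runs through that visit (Protocol Table 16), which narrows the gap, although Protocol 18.3.2 still refers to 30 days after last dose. The time-adjusted rates in SAP 6.8.1 lose patient-time along with events.

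**Two stronger readings are not supported.**
- A reader might infer that allowed local treatment closes the period while a man is still on study drug, since Protocol 7.2 says "Localized anticancer therapy (eg, topical treatment of non-melanoma skin malignancy, intravesical Bacillus Calmette-Guerin [BCG] treatment) may be acceptable" and SAP 3.5 does not define the trigger. But SAP 3.2.1.3 and 6.2.3 tie new antineoplastic therapy to prostate cancer. SAP 3.2.1.3 takes it from a long-term follow-up CRF page, and Protocol 9.1.3.2 describes those data as covering therapy after study drug is discontinued. What is missing is a cross-reference.
- A reader might infer that more events are lost in the control arm because time to new therapy is a key secondary endpoint. That endpoint runs from randomization. The loss depends on the gap between last dose and new therapy, and the documents say nothing about that gap by arm.

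**Conclusion.** The mismatch is real and confined to serious events. If the earlier date governs, SAEs and AEs with fatal outcome that start on or after new therapy but within 30 days of last dose are collected, are treatment-emergent under Protocol 10.5, and are missing from the serious-TEAE tables. A patient who starts new therapy d days after last dose (1 to 30) loses 31 − d of 30 days, from all of them at d = 1 to one at d = 30.

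The trial-level effect cannot be derived. The documents give neither the number of patients switching within 30 days nor the SAE rate in that window, and they support no claim of bias toward either arm. The conclusion rests on the earlier-of reading, which the SAP does not state. The wording needs correcting on either reading, because the derivation is otherwise left to the programmer.

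**What to change.** - **Serious and fatal AEs (SAP 3.5 and 6.8.1).** Summarize them through 30 days after last dose regardless of new therapy, as in Protocol 10.5. Make this the main serious-TEAE table, or add it beside the truncated one. Footnote that some events after the switch may be due to the new therapy. Any time-adjusted rate for these events should use patient-time over the same window.
- **Non-serious AEs.** Keep the cut, because Protocol 8.1.6 stops their recording at new therapy and a longer window would add time without data. State *whichever occurs first*, and tie the triggering therapy to the prostate-cancer definition in SAP 3.2.1.3 and 6.2.3.
- **Cross-reference.** In SAP 6.8, point to section 3.5 instead of 5.2.5 for the on-treatment period.

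The cost is SAP wording, one re-derived flag and possibly one extra table, all on data the protocol already requires. The drawback is that serious and non-serious events would follow different windows. That reflects how the protocol collects them, and showing both serious-event tables makes the difference visible.
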